#### 4 STUDY POPULATION

#### 4.1 **Inclusion Criteria**

- 1. Adult male or female aged 18 years or older.
- 2. Have a histologically or cytologically confirmed unresectable and/or metastatic solid tumour and who have received or been intolerant to all curative treatment options and for whom AGI-134 is a reasonable option for treatment.
- 3. Subjects should have at least two lesions that are evaluable (based on RECIST v1.1, as determined by the site study team) and that can be assessed for abscopal effect and from which a biopsy can be taken. Superficial large lesions of more than 25 cm can be considered as two lesions upon discussion with and approval by the Sponsor.
- 4. For a subject to be eligible the following is required:

#### Part 1:

- Unresectable superficial/palpable tumour feasible for intratumoural injection from any solid tumour, and
- A metastatic/secondary lesion that can be assessed for abscopal effect and from which a biopsy can be taken.

At least one unresectable lesion feasible for intratumoural injection and biopsy, and

Protocol AGI-134.FIM.101 CONFIDENTIAL Page 36 of 108

<sup>7 Tumour lesions situated in a previously irradiated area are considered evaluable if progression has been demonstrated in such lesions.

agalin A subsidiary of BIO		PRIVILEGED & CONFIDENTIAL
Investigational Product: AGI-134	designed to evaluate the safety and tolerability of escalating doses of AGI-134 in unresectable/metastatic solid tumours.	Protocol No. AGI-134.FIM.101
Phase: I/IIa		Version 6.1 31 May 2021

- A metastatic/secondary lesion that can be assessed for abscopal effect and from which a biopsy can be taken. The lesions should be from one of the following selected metastatic tumours:
- The lesions should be from one of the following selected metastatic tumours:
  - Skin melanoma patients with progression on up to two lines immunotherapy, whether or not patient was previously treated with chemotherapy or targeted therapy.
  - Patients with superficial (either visible or palpable) lesions that can be injected and biopsied from the following indications:
    - a. Skin melanoma treated with three previous lines of immunotherapy, upon discussion and approval by the Sponsor.
    - b. Any squamous cell carcinoma (SCC)
    - c. Mucosal melanoma
    - d. Other Skin cancers, such as: Basocellular carcinoma, Merkel cell carcinoma
    - e. Any other superficial/palpable tumour, either primary or metastasis that are available for injection and biopsy upon discussion with and approval by the Sponsor.
- 5. Patients who received prior treatment with CPI should have remained on treatment with one of the immunotherapy treatments for at least 4 months or have stopped treatment earlier than that due to toxicity rather than disease progression.
- 6. Subjects who are willing to undergo tumour biopsies, according to protocol requirements.
- 7. Tumour size:
  - O Part 1: The total size of the tumour(s) should allow injection of the total volume required at each escalation cohort. The volume can be injected into one lesion or divided into more than one lesion, but the total volume should be given according to the total dose at each escalation part. When volume is divided between several tumours, at least 1 mL should be injected into each tumour.
  - o Part 2: Tumour dimensions should allow injection of a minimum of 1 mL.
- 8. Has  $\geq$  2 lesions
  - Has ≥1 injectable lesion which is amenable to injection and biopsy and is evaluable according to RECIST v1.1.
  - Has another lesion which is amenable for biopsy and is evaluable according to RECIST v1.1. Superficial large lesions of more than 25 cm can be considered as two lesions upon discussion with and approval by the Sponsor.
- 9. Evaluable Disease according to RECIST v1.1
- 10. Has an Eastern Cooperative Oncology Group (ECOG) Performance Status score of 0 or 1.
- 11. Has a life expectancy >3 months

		PRIVILEGED & CONFIDENTIAL
Investigational Product: AGI-134		Protocol No. AGI-134.FIM.101
Phase: I/IIa		Version 6.1 31 May 2021

- 12. Adequate organ function at Screening as defined below. All laboratory assessments should be performed within 10 days prior to treatment initiation.
  - o Haematology:
    - White blood cell (WBC)  $\geq 2,500/\text{mm}^3$
    - Absolute neutrophil count ≥ 1500 /mm^3
    - Platelet count  $\geq 100,000/\text{mm}^3$
    - Haemoglobin ≥9 g/dL or ≥5.6 mmol/L
    - Haematocrit >30%
  - Renal function:
    - Creatinine ≤1.5x Upper limit of normal (ULN) OR measured or calculated creatinine clearance (glomerular filtration rate [GFR]) can also be used in place of creatinine or CrCl) > 50 mL/min for subject with creatinine levels > 1.5x institutional ULN
  - o Hepatic function:
    - Total Bilirubin: ≤1.5xULN OR Direct bilirubin ≤ULN for subjects with total bilirubin levels >1.5xULN
    - AST (SGOT) and ALT (SGPT): ≤2.5xULN OR ≤5xULN for subjects with liver metastases
  - Coagulation
    - International Normalised Ratio (INR) or Prothrombin Time (PT): ≤1.5xULN unless subject is receiving anticoagulant therapy as long as PT or PTT is within therapeutic range of intended use of anticoagulants
    - Activated Partial Thromboplastin Time (aPTT): ≤1.5xULN unless subject is receiving anticoagulant therapy as long as PT or PTT is within therapeutic range of intended use of anticoagulants
- 13. Women of childbearing potential and all men must agree to use 2 methods of an adequate contraception: One barrier method (e.g. diaphragm, or condom or sponge, each of which are to be combined with a spermicide) and one hormonal method (e.g. oral, transdermal patch, implanted contraceptives or intrauterine device) prior to study entry and for the duration of study participation through 120 days after the last dose of study treatment. Subjects that are highly unlikely to conceive (e.g. surgically sterile, postmenopausal, or not heterosexually active) are exempt. Confirmation that female subjects are not pregnant must be established by a negative serum β-human chorionic gonadotropin (βhCG) pregnancy test result obtained during Screening. Pregnancy testing is not required for postmenopausal or surgically sterilised women.

Non-childbearing potential is defined as (by other than medical reasons):

• ≥45 years of age and has not had menses for over 2 years.

agalin A subsidiary of Bio	nnune DLINERX	PRIVILEGED & CONFIDENTIAL
Investigational Product: AGI-134		Protocol No. AGI-134.FIM.101
Phase: I/IIa		Version 6.1 31 May 2021

 <45 years of age and amenorrhoeic for > 2 years without a hysterectomy and oophorectomy and a Follicle Stimulating Hormone (FSH) value in the postmenopausal range upon pre-trial (screening) evaluation.

For women, post hysterectomy, bilateral oophorectomy, bilateral salpingectomy or bilateral tubal ligation and vasectomy for men at least 6 weeks prior to screening. Documented hysterectomy or oophorectomy must be confirmed with medical records of the actual procedure or confirmed by ultrasound. Tubal ligation must be confirmed with medical records of the actual procedure.

- 14. Subject is able and willing to comply with the requirements of the protocol.
- 15. Subject is able to voluntarily provide written informed consent.

#### 4.2 Exclusion Criteria

Subject must be excluded from participating the study if he/she:

- 1. Has a disease that is suitable for therapy administered with curative intent.
- 2. Has any active, acute, or chronic infection(s) that are uncontrolled and/or requiring treatment, such as antibiotics
- 3. An active autoimmune disease that has required systemic treatment in the 2 years preceding the study (i.e., with the use of disease-modifying agents, corticosteroids or immunosuppressive drugs). Note: Replacement therapy (e.g., thyroxine, insulin, or physiologic corticosteroid replacement therapy for adrenal or pituitary insufficiency, etc.) is not considered a form of systemic treatment and is allowed.
- 4. History of or plan for splenectomy or splenic irradiation
- 5. History of organ transplant or currently taking active immunosuppressive therapy such as cyclosporine, tacrolimus, etc.
- 6. Has a known history of Human Immunodeficiency Virus (HIV) (HIV 1/2 antibodies).
- 7. Has known active Hepatitis B (e.g., Hepatitis B Surface Antigen [HBsAg] reactive) or Hepatitis C (e.g., Hepatitis C Virus [HCV] RNA [qualitative] is detected).
- 8. Has known Chronic Hepatitis B or C.
- 9. History or evidence of cancer associated with immunodeficiency states (e.g. hereditary immune deficiency, organ transplant, or leukaemia)
- 10. Has a diagnosis of immunodeficiency or is receiving systemic steroid therapy or any other form of immunosuppressive therapy within 7 days prior to the first dose of study treatment.
- 11. Is expected to require any other form of antineoplastic therapy while on study.
- 12. Has positive IgE anti-Gal
- 13. Subject has a known allergy to alpha-Gal, such as red meat allergy, exposure to lone star tick (Amblyomma americanum), Ixodes ricinus/ holocyclus.
- 14. Has known allergy or hypersensitivity to any of the test compounds, materials or contraindication to test product

agalin A subsidiary of Bio		PRIVILEGED & CONFIDENTIAL
Investigational Product: AGI-134	A Phase I/IIa, multicentre, two-parts, open label study designed to evaluate the safety and tolerability of escalating	Protocol No. AGI-134.FIM.101
Phase: I/IIa	doses of AGI-134 in unresectable/metastatic solid tumours.	Version 6.1 31 May 2021

- 15. History or evidence of central nervous system metastases and/or carcinomatous meningitis (unless stable without treatment for at least 6 weeks and not requiring steroids)
- 16. Has received other experimental therapies or used an investigational device within 28 days of the first dose of treatment
- 17. Has had prior chemotherapy, targeted small molecule therapy, or radiation therapy within 14 days before first AGI-134 administration or has not recovered from treatment related AE> Grade 19
- 18. Has had a prior anti-cancer monoclonal antibody (mAb) within 28 days before first AGI-134 administration or who has not recovered from AE > Grade 1.
- 19. Is pregnant or breastfeeding or expecting to conceive or father children within the projected duration of the study, starting with the Screening visit through 120 days after the last dose of study treatment. Women with a positive pregnancy test within 72 hours from Baseline.
- 20. Has unstable angina, new onset angina within the last 3 months, myocardial infarction within the last 6 months, uncontrolled atrial fibrillation, or current congestive heart failure with New York Heart Association Class III or higher.
- 21. Has a known current additional malignancy that is progressing or requires active treatment. Exceptions are non-melanoma skin lesions, adequately treated basal cell or squamous cell carcinoma that has undergone potentially curative therapy or carcinoma in situ of the cervix.
- 22.  $O_2$  saturation < 92% (on room air).
- 23. Has an underlying medical condition that would preclude study participation or other psychological, social or physical examination (PE) finding or a laboratory abnormality that the PI considers would make the subject a poor study candidate or could interfere with protocol compliance or the interpretation of study results.
- 24. Has known psychiatric or substance abuse disorders that would interfere with cooperation with the requirements of the study.

### 4.3 Subject Identification

Each consented subject will receive a unique subject number that will be used to identify the subject for all procedures that occur from Screening throughout the end of study or until the subject terminates from the study. Each subject will be assigned only one subject number. Subject numbers must not be re-used for different subjects.

Any subject who is rescreened will be assigned with a new subject number. Both numbers will be documented in the eCRF for traceability purposes.

\_

<sup>8 Note: Subjects with previously treated brain metastases may participate, provided they are stable (without evidence of progression by imaging using the identical imaging modality for each assessment, either MRI or CT scan, for at least four weeks prior to the first dose of study treatment and any neurologic symptoms have returned to baseline), have no evidence of new or enlarging brain metastases, and are not using steroids for at least 7 days prior to study treatment. This exception does not include carcinomatous meningitis which is excluded regardless of clinical stability

<sup>9 Subjects with ≤ Grade 2 neuropathy or ≤ Grade 2 alopecia are an exception to this criterion and may qualify for the study. If subject underwent major surgery, they must have recovered adequately from the toxicity and/or complications from the intervention prior to starting therapy.

agalin A subsidiary of Bio	DINE X	PRIVILEGED & CONFIDENTIAL
Investigational Product: AGI-134		Protocol No. AGI-134.FIM.101
Phase: I/IIa		Version 6.1 31 May 2021

Specific details on the Screening visit requirements (Screening/rescreening) are provided in Section 5.1.

## 4.4 Screening Failure

Subjects who fail to meet the inclusion criteria at any stage during the Screening period are defined as screening failures. All screening failures will be documented on the appropriate log which will be kept in the Investigator's Site File. Subjects who failed the screening procedures may be rescreened after consultation with the Sponsor. Rescreening procedures are detailed in Section 5.1.

## 4.5 Removal, Replacement or Early Withdrawal of Subjects from Therapy or Assessment

Subjects are free to discontinue the investigational product and/or their participation in the study at any time and without prejudice to further treatment. The PI must withdraw any subject from the study if that subject requests to be withdrawn, or if it is determined that continuing in the study would result in a significant safety risk to the subject. Subjects that discontinue the investigational product will continue to participate in the Long-Term Follow-up of the study for 5 years, unless they withdraw their consent to continue their participation in the study as well.

Subjects withdrawn from the study prior to the Baseline visit, prior to first injection of AGI-134 or before completion of the DLT assessment period (see Section 3.1.1) will be replaced by the PI to achieve the appropriate number of subjects, regardless of the reason for withdrawal. All data, regardless of DLT period completion or not, will be part of the safety cohort assessment.

If a subject discontinues from the study during the DLT assessment period for any reason other than safety, a replacement subject may be enrolled if deemed appropriate by the PI and Sponsor in order to reach the target number for DLT assessment. Subjects who discontinued the study during the DLT period because of progression will not be considered for DLT assessment; however, they will be counted as having progressed for the efficacy analysis. The replacement subject will be assigned with a unique subject number.

The subject's use of investigational product may be discontinued for any of the following reasons:

- Investigational product toxicity (adverse drug reaction)
- Death
- · Request of regulatory agency
- · Sponsor's request
- PI's request: Investigator decides that withdrawal from the study is in the best interest of the subject
- · Withdrawal of consent by the subject
- Disease Progression
- Female subject who becomes pregnant
- Lost to follow-up

agalin A subsidiary of Bio	nnune DLINERX	PRIVILEGED & CONFIDENTIAL
Investigational Product: AGI-134		Protocol No. AGI-134.FIM.101
Phase: I/IIa		Version 6.1 31 May 2021

- · Subject is non-compliant with study procedures/study protocol
- Other

## 4.6 Handling Withdrawals

If a subject is withdrawn from the study, every effort should be made to determine the reason. This information will be recorded on the subject's eCRF. All subjects who withdraw from the study prematurely, regardless of cause, should undergo all Early Termination study visit procedures (see Section 5.4), followed by a Long-Term Follow-Up.

If withdrawal is caused by an AE that the PI considers as probably related to the investigational product, the AE will be reported to the institutional review board/independent ethics committee (IRB/IEC) as per local national and site guidelines.

All AEs will be followed-up with appropriate medical management until the outcome is determined or stabilised, according to the PI's clinical judgement. All follow-up information will be recorded in the subject's eCRF until resolution of the AE.

Any SAE must be reported to the Sponsor or Sponsor's designee by telephone, fax or email within 24 hours of the PI's becoming aware of the event and to the IRB/IEC according to local regulations (for notification of SAE, refer to Section 7.2.5).

## 4.7 Termination of Study

The Sponsor reserves the right to discontinue the study at any time at the participating sites for any reason.

Regulatory Authorities also have the right to terminate the study for any reason.

## 5 STUDY PROCEDURES AND ASSESSMENTS

The Schedule of Assessments (SoA) for this study is shown in APPENDIX A. No protocol-related procedures should be performed before the subject provides a written informed consent. Study-related events and activities (including specific instructions, procedures, concomitant medications, dispensing of study medication, and descriptions of AEs) should be recorded in the appropriate source documents and eCRF.

## 5.1 Screening Period (Day -28 To Day 0)

At the Screening visit, the purpose and procedures of the study will be fully explained to the subjects. Those wishing to participate in the study will sign a written Informed Consent Form (ICF) prior to initiating any evaluations or study-related procedures. After signing ICF, male and female subjects aged ≥18 years will be screened for study eligibility by assessment of Inclusion and Exclusion criteria. All the assessments should be completed during the Screening period and up to the Baseline visit-Day 0.

agalin A subsidiary of BIG	nnune BLINERX	PRIVILEGED & CONFIDENTIAL
Investigational Product: AGI-134		Protocol No. AGI-134.FIM.101
Phase: I/IIa		Version 6.1 31 May 2021

A window of up to 28 days is allowed for the Screening period procedures, from the time of ICF signature until Day 0 - Baseline visit (before dosing), with the exception of all safety laboratory assessments (Complete Blood Count (CBC), Biochemistry, coagulation test), which should be completed within 10 days prior to first AGI-134 administration. Eligibility information will be sent to the Sponsor for review and approval prior to subject's entry into the study.

## **Screening Procedures:**

- ICF signature
- Inclusion/Exclusion Criteria review
- Collection of demographic data
- Collection of medical history
- Collection of disease history (including genetic information, dMMR/MSI/TMB)
- Collection of disease treatment history
- Review of prior (up to one year) and concomitant medications
- AE recording
- 12-lead electrocardiogram (ECG) local reading
- Full physical examination
- Vital signs (blood pressures, pulse rate, O2 saturation, oral temperature in °C, respiratory rate)
- Weight
- Height
- Urinalysis
- ECOG performance status
- Blood will be drawn for:
  - o Serum pregnancy test
  - o FSH for women who reported menopause for less than two years
  - o Disease markers according to each subject's disease
  - HPV status for relevant indications (HPV status assessment should be performed at local lab in case no available status from the time of diagnosis)
  - PT/INR and Activated Partial Thromboplastin Time (aPTT)
  - CBC with differential
  - Biochemistry panel
  - o T3, free T4 and thyroid stimulating hormone (TSH)
  - o HIV, HBV and HCV serology

<sup>10 For subjects on anticoagulant treatment, coagulation test should be performed within 24 before the injection and biopsy at Baseline. Anticoagulants should be stopped for injection and biopsy according to institutional guidelines.

<sup>11 The coagulation test should be within normal limits unless the subjects are being treated with an anticoagulant in which case the values allowed for injection and biopsy as well as the timing to stop anticoagulants before injection and biopsy will be determined at each site according to institutional guidelines.

agalin A subsidiary of BIO		PRIVILEGED & CONFIDENTIAL
Investigational Product: AGI-134		Protocol No. AGI-134.FIM.101
Phase: I/IIa	doses of AGI-134 in unresectable/metastatic solid tumours.	Version 6.1 31 May 2021

- o Blood for anti-Gal IgE
- Tumour imaging. A standard of care imaging performed prior to ICF signature, which were done according to the imaging manual guidelines (Please refer to the *Imaging Manual* for more details) and are within the screening window will be allowed for eligibility.
- RECIST v.1.1 assessment

Subjects may be rescreened after consultation with the Sponsor.

## **Rescreening Procedures:**

- New ICF signature
- Inclusion/Exclusion Criteria review
- AE recording
- 12-lead electrocardiogram (ECG) local reading
- Full physical examination
- Vital signs (blood pressures, pulse rate, O2 saturation, oral temperature in °C, respiratory rate)
- Weight
- Urinalysis
- ECOG performance status
- Blood will be drawn for:
  - Pregnancy test in serum
  - Disease markers will be collected according to each subject's disease
  - PT/INR and Activated Partial Thromboplastin Time (aPTT)
  - o CBC with differential
  - Biochemistry panel
- Tumour imaging will be required upon consultation with the Sponsor's Medical Monitor

## 5.2 Baseline Visit (Day 0)

Baseline visit (Day 0) procedures occur **before** administration of the investigational product. A window of 3 days is allowed for the procedures and assessments of this visit.

#### **Baseline Procedures:**

- Inclusion/Exclusion Criteria re-assessment
- Review of change in concomitant medication
- AE recording
- Symptom-Directed physical examination
- Urinalysis
- Pregnancy test in urine
- Blood will be drawn for:
  - o PT/INR and aPTT (results should be available before injection)

agalin A subsidiary of BIO		PRIVILEGED & CONFIDENTIAL
Investigational Product: AGI-134	designed to evaluate the safety and tolerability of escalating	Protocol No. AGI-134.FIM.101
Phase: I/IIa		Version 6.1 31 May 2021

- o CBC with differential
- o Biochemistry Panel
- Biopsies can be performed within 7 days before the first dose of AGI-134 or on the same day of treatment prior to AGI-134 administration. Please refer to the instructions included in the Administration of AGI-134 and Tumour Biopsy Procedures in Study AGI-134.FIM.101 document. Two biopsies should be performed:
  - From the tumour lesion to be injected
  - o From an un-injected lesion

Note that dMMR/MSI/TMB assessment may be performed on the collected biopsy and blood sample by the central lab if not available within the Subject's medical history.

It is the Investigator's responsibility to instruct the Subject to contact the site for any changes in his/her well-being. In such cases, Investigator must obtain information regarding concomitant medication changes and adverse events.

## 5.3 Core Study

The duration of the Core Study will be up to 54 weeks.

AGI-134 administration is divided into cycles (each cycle is 3 weeks long). Each cycle may be extended if additional safety assessment is needed.

AGI-134 is administered for up to 4 cycles. For administration and tissue biopsies information and guidance, please refer to the instructions in the *Administration of AGI-134 and Tumour Biopsy Procedures in Study AGI-134.FIM.101* document.

Visits will be named as follows:

- AGI-134 Administration Visits: Visit Cycle 1-Day 1, Visit Cycle 2-Day 1, Visit Cycle 3-Day 1, Visit Cycle 4-Day1
- Other Visits:
   Visit Cycle 1-Day 3, Visit Cycle 1-Day 8, Visit Cycle 1-Day 15, Visit Week 18,
   Visit Week 27, Visit Week 36, Visit Week 45, Week 54 (Termination)

## 5.3.1 Cycle 1

This visit will begin after completion of the Baseline visit. Treatment initiation may be done on the same day of Baseline visit, but Baseline procedures should be completed prior to investigational product administration. On this day, AGI-134 will be administered. The following activities will be performed during this visit. Details on the specific days for each assessment are presented in the SoA (APPENDIX A).

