## Week 18, 27, 36 and 45 Visits

Visits will be performed at the following weeks: 18, 27, 36 and 45 (i.e. every 9 weeks beginning from Cycle 4).

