## Week 18, 27, 36 and 45 Visits Procedures:

- Review of change in concomitant medication
- AE Recordings (AEs up to 30 days post last dose of study drug and SAEs up to 90 days post last dose of study drug)
- Examination of injection site
- ECOG performance status
- Photography pictures of all injected superficial tumour, if applicable.
- Tumour Imaging assessment
- RECISTv.1.1 assessment will be done using imaging and/or superficial lesion measurement according to the tumour type.

agalin A subsidiary of BIO		PRIVILEGED & CONFIDENTIAL
Investigational Product: AGI-134	A Phase I/IIa, multicentre, two-parts, open label study designed to evaluate the safety and tolerability of escalating	Protocol No. AGI-134.FIM.101
Phase: I/IIa	doses of AGI-134 in unresectable/metastatic solid tumours.	Version 6.1 31 May 2021

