## 5.4 Termination or Early Termination Study Visit (Week 54 or ET)

The total study participation period is 54 weeks. Treatment with AGI-134 will be provided for up to 4 cycles (12 weeks). A Termination visit will be performed at Week 54 for all subjects.

In case of Early Termination (ET), all reasons for treatment discontinuation will be documented in the source documents yet only one reason (the most severe) for ET should be recorded in the eCRF. If one of the reasons for early termination is an AE, this should be chosen as the reason. Every effort should be made to follow-up these subjects until resolution or stabilisation of the AE.

At this visit, the following activities will be performed. Exceptions for assessments may be provided in case these assessments were done 1-2 cycles prior to Termination visit and after discussion and approval by the study MM.

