# 8.2.2 Analysis of Safety and Tolerability

Safety parameters (vital signs and laboratory results) will be summarised in listings and presented in tables as changes from Baseline.

ECG examinations results will be displayed in descriptive tables provide the frequency of subjects with abnormal findings for each schedule visit.

AEs will be coded using the latest version of MedDRA (currently version 24.0) and presented in tables by system organ class (SOC), HLT and preferred term. The worst severity grade of AEs, as determined by the latest version of the NCI-CTCAE (currently version 5.0), and their relationship to investigational product will be analysed by SOC, High Level Terms and Preferred Term.

The action taken, and outcome will also be analysed.

By-subject list of AEs, severity grade and relationship will be presented in time-sequence manner using the latest version of NCI-CTCAE (currently 5.0) with SOC, High Level terms and Preferred Term. The number and incidence of subjects experiencing toxicity will be tabulated by worst severity grade in each MedDRA term. The proportion of subjects experiencing toxicity  $\geq$  Grade 3 for each type of toxicity will be calculated.

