# 12 APPENDICES

APPENDIX A: Schedule of Assessments

agalin A subsidiary of BIG		PRIVILEGED & CONFIDENTIAL
Investigational Product: AGI-134	A Phase I/IIa, multicentre, two-parts, open label study designed to evaluate the safety and tolerability of escalating doses of AGI-134 in unresectable/metastatic solid tumours.	Protocol No. AGI-134.FIM.101
Phase: I/IIa		Version 6.1 31 May 2021

Table 6: Schedule of Assessment - Part 1: Accelerated Dose Escalation of AGI-134

Study Period:	Screening Phase	Baseline Assessments					3-	We	ek (	Cyc	les				9-Week F.U Cycles	Termination Visit	Long-Term Follow-up
Treatment Cycle:	Screening (Visit 1)	Pre-Dose	Cycle 1		1	C	Cycle 2		С	Cycle 3			cle	4	Weeks 18, 27, 36 & 45	Week 54 or early Termination	Survival Follow-up call
Days from injection (Safety assessment follow-up)	-28	0	1	8	15	1	8	15	1	8	15	1	8	15			
Scheduling Window (Days) unless specified otherwise	-28 to 0	-3 to 1 Pre- dose		+3			±3			±3			±3		±3	±3	Every 9 weeks (±7 days)
Informed Consent	X																
Inclusion/Exclusion Criteria	X	X 								Г							
Demographics and Medical History	X																
Disease history (including genetic information, dMMR/MSI and Tumour Mutational status)	Х																
Disease treatment history	X																
Prior and Concomitant Medication Review	X	X	X	X	X	X	X	X	X	X	X	X	X	X	Х	X	
Review Adverse Events	X	X	X	X	X	X	X	X	Х	X	X	X	X	X	X	X	
12-Lead Electrocardiogram (ECG) local reading	X		X 			X 			X 			X 				X	
12-Lead Electrocardiogram (ECG) central reading			X 									X3					
Full Physical Examination	X					Ī				Ī	1					X	

agalin A subsidiary of Bio		PRIVILEGED & CONFIDENTIAL
Investigational Product: AGI-134	A Phase I/IIa, multicentre, two-parts, open label study designed to evaluate the safety and tolerability of escalating doses of AGI-134 in unresectable/metastatic solid tumours.	Protocol No. AGI-134.FIM.101
Phase: I/IIa		Version 6.1 31 May 2021

Study Period:	Screening Phase	Baseline Assessments					3-	We	ek (	Сус	les				9-Week F.U Cycles	Termination Visit	Long-Term Follow-up
Treatment Cycle:	Screening (Visit 1)	Pre-Dose	Cycle 1			C	Cycle 2			Cycle 3			ycle	4	Weeks 18, 27, 36 & 45	Week 54 or early Termination	Survival Follow-up call
Days from injection (Safety assessment follow-up)	-28		1	8	15	1	8	15	1	8	15	1	8	15			
Scheduling Window (Days) unless specified otherwise	-28 to 0	-3 to 1 Pre- dose		+3			±3			±3			±3		±3	±3	Every 9 weeks (±7 days)

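### Part 2 schedules no contact between the dosing day of dose 4 and the end of the 30-day AE window, and neither part schedules routine CBC or biochemistry after dose 4 before Week 54 or Early Termination

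*Combined protocol and SAP*

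**What the plan says.** **Visits.** Section 5.3 names the dosing visits as "Visit Cycle 1-Day 1, Visit Cycle 2-Day 1, Visit Cycle 3-Day 1, Visit Cycle 4-Day1" and begins the other visits with "Visit Cycle 1-Day 3, Visit Cycle 1-Day 8, Visit Cycle 1-Day 15, Visit Week 18". For the later visits it says "Visits will be performed at the following weeks: 18, 27, 36 and 45 (i.e. every 9 weeks beginning from Cycle 4". This list is not limited to one part. Table 7 (Part 2) agrees with it: there is one Cycle 4 column and no Day 8 or Day 15 after Cycle 1. Table 6 (Part 1) does not. Its row "Days from injection (Safety assessment follow-up" gives Days 1, 8 and 15 in every cycle. The Cycle 4 Day 8 and Day 15 columns carry AE review, directed examination, injection-site examination, photography and vital signs.

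**Content.** Under Section 5.3.4, Cycle 4 CBC, biochemistry and coagulation are taken before the dose. After the dose there are an injection-site examination and photography at 1 hour, and vital signs and an ECG at 2 hours. The Week 18 to 45 visits record "AEs up to 30 days post last dose of study drug" and SAEs to 90 days, but list no vital signs, CBC or biochemistry. Those return in Section 5.4, at Week 54 or Early Termination.

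**Analysis.** Section 8.2.2 states: "Safety parameters (vital signs and laboratory results) will be summarised in listings and presented in tables as changes from Baseline". The predefined populations in Section 8.2 are all of Part 1, Parts 1 and 2 together, and a Part 2 melanoma subgroup. Part 2 as a whole is not listed.

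**The concern.** Safety and tolerability are the primary objective of this first-in-human study. In Part 2, the first scheduled question about non-serious events after dose 4 comes weeks after the collection window has closed. Short or mild events, and their dates and grades, are the ones most easily lost over such an interval, so the likely error is an incidence after dose 4 that is too low. Part 1 subjects, on Table 6, are asked 7 and 14 days after the same dose. A pooled AE rate then depends partly on how closely each part was watched.

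The laboratory gap has a different consequence. An asymptomatic change in blood count or chemistry after the dose with the greatest cumulative exposure has no routine test that would show it while it could still be linked to treatment.

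**Working it through.** **Inputs**

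- Cycle length, Section 5.3: "AGI-134 administration is divided into cycles (each cycle is 3 weeks long".
- Treatment length, Section 5.4: "Treatment with AGI-134 will be provided for up to 4 cycles (12 weeks".
- AE window 30 days and SAE window 90 days after the last dose, each ending sooner if new anti-cancer therapy starts (Section 7.1).
- Visit windows of ±3 days at Cycle 4 and Week 18 (Table 7).
- Permitted dosing interruption of 3 weeks (Section 6.7.4).
- Planned numbers: about 35 in Part 2, up to 24 in Part 1.

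**1. Reproduce the plan's calendar.** Dose k falls on Day 1 + 21 × (k − 1), that is Days 1, 22, 43 and 64. Cycle 4 then covers Weeks 10 to 12 and four cycles take 12 weeks, as stated. Nine weeks after dose 4 is Day 64 + 63 = Day 127, or 18 elapsed weeks, which matches the Week 18 label.

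**2. Close of the windows.** AEs: 64 + 30 = Day 94. SAEs: 64 + 90 = Day 154.

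**3. Distance from dose 4 to Week 18.** The label can mean the start of the 18th week (Day 120) or 18 weeks elapsed (Day 127).

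| Case | Days after dose 4 | Days after the AE window closes |
|---|---|---|
| On schedule | 120 − 64 = 56 to 127 − 64 = 63 | 26 to 33 |
| With ±3 days on both visits | 56 − 6 = 50 to 63 + 6 = 69 | 20 to 39 |
| One 3-week delay, Week 18 counted from Day 1 | 56 − 21 = 35 to 63 − 21 = 42 | 5 to 12 |

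With that delay and both visit windows at their extreme, the distance is 35 − 6 = 29 days, the only one of these cases that reaches the window. If Week 18 is counted from Cycle 4, a delay does not shorten the distance. In every case Week 18 lies inside the 90-day SAE window.

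**4. Comparison with Part 1.** Cycle 4 Day 8 and Day 15 are Days 64 + 7 = 71 and 64 + 14 = 78. Both lie inside the AE window.

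**5. Laboratory tests.** Dose 1 is followed by tests on Days 3, 8 and 15 in Part 2, and each of doses 1 to 3 by the next cycle's pre-dose tests 21 days later. Dose 4 has no next cycle. Week 54 is Day 372 to Day 379, so 372 − 64 = 308 to 379 − 64 = 315 days, or 44 to 45 weeks, after dose 4. Table 6 marks Cycle 4 CBC and biochemistry on Day 1 only, so Part 1 has the same gap.

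**6. Share affected.** If all 35 Part 2 subjects received four doses and stayed on study, 35 of 35 × 4 = 140 administrations (25%) would have no routine test before Week 54. This is an upper bound. At planned numbers, Part 2 supplies at least 35 / (35 + 24) = 59% of the pooled population.

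**The case against.** A reader might infer that toxicity after dose 4 is largely unobserved, that no laboratory result after it can reach a table, or that nothing is drawn until Week 54. The documents support none of these.

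- Checks at 1 and 2 hours after dose 4 fall inside the window, so the gap starts after the dosing day.
- Early Termination carries CBC, biochemistry and thyroid tests, and Section 4.6 requires its procedures after any premature withdrawal. The 44 to 45 weeks apply only to subjects who remain to Week 54. An Early Termination visit can fall inside the AE window, but its timing is not tied to the last dose.
- Week 18 does collect AEs from the 30-day window, and the SAE window is then still open. Section 5.2 has subjects told to contact the site about changes in well-being. Section 5.8.1 requires AEs between visits to be brought to the investigator.
- Section 5.6 allows unscheduled visits with safety laboratory tests, and Section 5.8.6 requires clinically significant abnormal results to be reported as AEs. Such results can be tabulated. What is likely to be missed is the asymptomatic change that prompts no visit.
- The laboratory gap is the same in both parts, so pooling mixes levels of clinical AE observation but not of routine laboratory testing.
- Section 8.2 lists Part 1 as its own population, and the synopsis has AE tables by dose level. These separate the parts to some degree, but a Part 1 cohort treated at the RP2D could share a dose level with Part 2.
- Section 1.1.1 reports no drug-related haematology or coagulation changes, and no definite chemistry changes, after five weekly doses in monkeys. This weakens the case for an extra blood draw.

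All of this stands and limits the point. It does not supply a scheduled contact inside the window: the routes that remain depend on the subject calling, the investigator's discretion, or memory at 8 to 9 weeks.

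**Conclusion.** The point holds in limited form. On schedule, a Part 2 subject who stays on study has no planned contact from the end of the dosing-day checks on Day 64 until 56 to 63 days after dose 4 (50 to 69 with visit windows), although the AE window closes at 30 days. Non-serious AEs after dose 4 are therefore probably under-ascertained in Part 2 relative to Part 1, and the pooled rate combines the two. The direction is a judgement about recall; the documents give nothing from which to estimate its size. Routine laboratory follow-up of dose 4 is absent in both parts until Week 54 or Early Termination.

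This assumes that Table 6 was followed in Part 1 and that dosing kept to schedule. One 3-week delay with Week 18 counted from Day 1 narrows the interval to 35 to 42 days, still beyond the window. Further delays or an extended cycle could narrow it more.

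**What to change.** 1. Add to Section 5.3 and Table 7 a telephone AE and concomitant-medication check at the end of the 30-day window after the last dose. Cost: one call per subject and a small amendment.
2. Report AE rates by part alongside the pooled rate, and state that dose 4 has no routine laboratory follow-up before Week 54 or Early Termination. Cost: additional tables and a sentence in the report.
3. Reconcile the Section 5.3 visit list with the Cycle 2 to 4 Day 8 and Day 15 visits in Table 6, so that it is clear which visits Part 1 subjects have.
4. Optionally, add local CBC and biochemistry after dose 4 in both parts, comparable to the tests that follow doses 1 to 3. Cost: one routine blood draw per subject who receives dose 4. This matters less than the first three.
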